8.2. Missing data

Primary analyses will be performed using all enrolled participants (intention-to-treat analysis). For the primary analysis, the proportion of patients with HBsAg loss at the end of follow-up (week 240) will be estimated using the product limit (Kaplan-Meier) method which includes drop outs for as long as they are followed. Since our sample size estimation accounts for participants lost to follow up for various reasons, and due to randomization, the rate of missing is expected to be similar in the two treatment groups, we will also conduct the analysis of primary endpoint on the available cases. For this analysis, we will describe the treatment effects in terms of relative risks and 95% confidence intervals. In order to take into account the stratification at the randomization, we will use Mantel-Haenszel chi-square test. Comparison of rates of HBsAg loss across two treatment groups adjusting for other baseline demographic, virological and clinical characteristics such as age, race, genotype, HBeAg status, initial HBV DNA level, and baseline histology will be performed using multivariable log-linear (Poisson) regression, with HBsAg loss (Yes/No) as the outcome. The results will be presented as relative risks of HBsAg loss and their 95% confidence intervals.

In general, the procedure of missing outcome data will be handled as follows in statistical analyses. First, we will explore the pattern of missing data by comparing characteristics of participants with available data to those with missing data. For data missing completely at random (does not depend on observed outcome; MCAR) standard analytical techniques described earlier would produce unbiased results when the analysis is performed on the complete data. For the time-to-event data analyses, the analytical methods such as Kaplan-Meier method, log-rank test, and Cox proportional hazard model automatically accounts for MCAR drop-outs. However, in other cases, we will assume that the dropout depends on observed outcome and/or covariates (missing at random, MAR). For such scenarios, likelihood-based methods such as mixed models, generalized linear mixed models and logistic regression will provide unbiased inference. For GEE, we will draw inference using inverse-probability-weighting approach, with models fitted using the reciprocal of the estimated probability of missing as weights. The probability of missing will be estimated using logistic regression.

It is unlikely that the probability of missing will depend on unobserved outcome and/or covariates (missing not at random, MNAR). However selection models such as MNAR Dale model and Diggle-Kenward model (23) can be used in such cases. These models often require strong assumptions on the dropout mechanism, which are primarily unverifiable based on the observed data. We will conduct sensitivity analyses to investigate the sensitivity of our conclusion to possible violation of such assumptions by fitting models under MCAR, MAR and MNAR assumptions and compare the model fits using log-likelihoods.

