The third group of variables consists of variables that are measured over time (longitudinal data) such as quantitative HBV DNA levels. For graphical representation over time, we will use spaghetti plots of original data (e.g. HBV DNA levels) and summarize the pattern of data across subgroups (e.g. genotype, treatment groups) over time by using means (for continuous outcome) or proportions (for binary outcomes). To determine the significance of change in continuous outcome over time across treatment group adjusting for other baseline and longitudinal participant characteristics, we will use mixed models if the data are normally distributed or generalized estimating equations (GEE) if deviation from normality is evidenced. These approaches simultaneously model the regression of the response variable on the independent variables and account for the correlated nature of the responses. Analyses using conventional regression methods could provide erroneous variance estimates and loss of statistical efficiency because of the conventional assumption that each response is statistically independent. As a result, invalid inferences could be made if the conventional approach were applied to these longitudinal data. A similar approach of analysis will be adopted (generalized linear mixed model or GEE) for longitudinal binary or count outcomes over time.

The results will be summarized using rate of change/odds ratio/relative risk over time and the corresponding confidence intervals. Interaction between treatment and participant characteristics will be investigated to assess the differential effect of treatments across subgroups of participants (e.g. genotypes).

Secondary endpoints that are defined within a specific subgroup will be analyzed only for participants in that subgroup. For example, sustained off treatment (36 and 48 weeks after end of treatment) responses will be assessed only among those whose treatment was discontinued at week 192.

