8.3. Sample size and power

The sample size for this study was determined based on the primary endpoint of HBsAg-loss at 48 weeks after treatment has been stopped. There are no data available on HBsAg loss for long-term treatment with tenofovir DF or tenofovir DF and peginterferon combination therapy. We anticipate that after 192 weeks of treatment and 48 weeks of follow-up post-treatment 5% of the participants in the tenofovir DF alone group will achieve HBsAg loss compared to 15% participants in the tenofovir DF and peginterferon combination therapy group. The clinical trial would require 141 participants per arm (282 participants in total) to detect this expected difference with 80% power at 5% level of significance using a two-sided test of equality between two proportions (chi-square test). However, for this long-term treatment trial, it is expected that approximately 25% of the participants will be lost to follow-up and hence the study will recruit a total of 376 participants (randomized 1:1 to two treatment arms, 188 per arm) to account for the missing participants.

9. Data and safety monitoring board

Data and safety will be monitored by the NIDDK in conjunction with an NIDDK-appointed Data and Safety Monitoring Board (DSMB). This board serves in a consultative capacity to inform the NIDDK decisions regarding conduct of the study. The description of DSMB activities is included in the DSMB Charter.

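### Section 8.2 inverts the inverse-probability weights for GEE: it weights observed records by 1/P(missing) where 1/P(observed) is needed

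*Combined protocol and SAP*

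**What the plan says.** Section 8.2 takes drop-out to be missing at random, depending on observed outcomes or covariates, wherever missing completely at random does not apply. It then gives the method: "For GEE, we will draw inference using inverse-probability-weighting approach", "with models fitted using the reciprocal of the estimated probability of missing as weights". The next sentence confirms which probability is meant: "The probability of missing will be estimated using logistic regression". Nothing else in section 8 redefines the weight, and the later paragraph on missing-not-at-random models does not return to it.

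Section 8.1.2.1 says where GEE is used. Continuous longitudinal outcomes, with quantitative HBV DNA as the example, go to mixed models, or to "generalized estimating equations (GEE) if deviation from normality is evidenced". For other outcome types it adds: "A similar approach of analysis will be adopted (generalized linear mixed model or GEE) for longitudinal binary or count outcomes over time". In section 8.3 (Sample size and power), "it is expected that approximately 25% of the participants will be lost to follow-up".

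**The concern.** Only observed records enter a GEE fit. Inverse-probability weighting corrects for missing-at-random drop-out by letting each observed record represent itself and the similar participants who were lost. Records from people likely to drop out must therefore be weighted up. The reciprocal of the probability of missing does the opposite. The fault is not one of scale: the ordering of the weights is reversed.

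The sentence governs the step meant to remove drop-out bias. Followed literally, that step typically makes arm-level bias larger than no weighting at all. If the drop-out pattern also differs by arm, it can distort the treatment contrast.

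**Working it through.** **Inputs from the plan.** 188 participants per arm and 25% loss, section 8.3 (Sample size and power). These agree with the plan's own figures: 282/0.75 = 376 in total, and 188 × 0.75 = 141 observed per arm. The plan gives no figure for the weights and no breakdown of the 25%, so everything below is a hypothetical illustration.

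**Step 1: the weights.** Let p be the probability of missing.

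| p | as written, 1/p | correct, 1/(1 − p) |
|---|---|---|
| 0.05 | 20 | 1.05 |
| 0.45 | 2.2 | 1.82 |

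**Step 2: an arm-level proportion.** Assume two equal groups, not in the outcome model, with response y of 90% and 50% (truth 70%) and missingness p1 and p2 averaging 25%. Each group contributes observed share 0.5(1 − p). The estimates are:

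- unweighted: Σ 0.5(1 − p)y / Σ 0.5(1 − p)
- as written: Σ 0.5[(1 − p)/p]y / Σ 0.5[(1 − p)/p]
- correct: Σ 0.5[(1 − p)/(1 − p)]y = 70% for every split

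For 10%/40%:

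- unweighted: (0.45 × 0.9 + 0.30 × 0.5)/0.75 = 0.740
- as written: (4.5 × 0.9 + 0.75 × 0.5)/5.25 = 0.843

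The effective sample size of the 141 observed is (Σw)²/Σw².

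| Missing in the two groups | Unweighted | As written | Correct | Effective n, as written | Effective n, correct |
|---|---|---|---|---|---|
| 25% / 25% | 70.0% | 70.0% | 70.0% | 141 | 141 |
| 20% / 30% | 71.3% | 75.3% | 70.0% | 135.7 | 140.4 |
| 10% / 40% | 74.0% | 84.3% | 70.0% | 110.5 | 135.4 |
| 5% / 45% | 75.3% | 87.6% | 70.0% | 100.4 | 131.0 |

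From 20%/30% to 5%/45%, the bias is 5.3 to 17.6 points as written and 1.3 to 5.3 unweighted. Bias is proportional to the response gap, so a 20-point gap halves it: 2.6 to 8.8 as written, 0.7 to 2.7 unweighted.

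**Step 3: the treatment contrast, with no true effect.**

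- Same split in both arms: 0 under all three methods.
- One arm 10%/40%, the other 20%/30%: as written 84.3 − 75.3 = 9.0 points; unweighted 74.0 − 71.3 = 2.7; correct 0.
- Group included in the model: 0.

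**Step 4: drop-out that depends on an earlier outcome.** Assume y1 = u + e1 and y2 = u + e2, all normal, with var(u) = 1, var(e) = 0.25 and true mean 0. Let logit P(y2 missing) = a + b·y1, with 25% missing and y1 not in the outcome model. Under the written weights an observed record counts in proportion to (1 − p)/p = exp(−a − b·y1). This shifts the mean of y2 by −b·cov(y1, y2) = −b.

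- b = 1, simulation of 200,000 per arm: mean y2 is −0.21 unweighted, −1.00 as written, 0.00 correct.
- Contrast, b = 1 in both arms: about 0 under all three.
- Contrast, b = 1 against b = 0.5: 0.08 unweighted, 0.49 as written (1.0 − 0.5 = 0.50 analytically), 0.00 correct.

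**Step 5: a weighted GEE at the trial's size.** 500 simulated trials of 376, about 23% missing, drop-out on an earlier outcome with a pattern that differs by arm, true arm difference −0.50. Estimates: −0.80 unweighted, −1.85 as written, −0.53 correct (Monte Carlo standard error at most 0.015). The small remaining gap for the correct weights is consistent with estimating the weights at this sample size.

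**The case against.** - **It is probably a wording slip.** The same passage names inverse-probability weighting, and most analysts would recognise what was meant. Literal use also gives extreme weights where p is near zero, which someone might notice. That is fair. But the logistic model the plan names returns P(missing), so inverting its output is exactly what the text instructs. An analyst who codes it correctly departs from the written plan.
- **Little may depend on it.** This stands. The items in sections 2.2.1 to 2.2.9 are fixed-time responses and rates, none of them a trajectory. GEE is conditional for continuous outcomes and optional for binary or count outcomes. Section 8.1 allows transformation of continuous variables, which could make GEE less likely still.
- **Covariates may absorb the drop-out.** Section 8.1.2.1 does plan adjustment for baseline and longitudinal characteristics of participants. This helps if every driver of drop-out is included, which is not guaranteed. Earlier values of the outcome are responses in such a model, so adjustment does not automatically cover them.
- **The contrast may be unbiased.** True when drop-out acts alike in both arms. Section 8.2 expects similar missing rates by arm, but similar rates do not imply similar patterns: both arms in Step 3 lose 25% on average.
- **The written weights are not always worse than none.** Correct. Take three equal groups missing 5%, 25% and 45% with response 40%, 95% and 0% (truth 45%). Unweighted: (0.95 × 0.40 + 0.75 × 0.95)/2.25 = 48.6%. As written: (19 × 0.40 + 3 × 0.95)/23.22 = 45.0%. The case is contrived, but enlarged bias is assured only when the outcome moves in one direction with missingness.

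**Conclusion.** The weight is wrong as written, and no other section corrects it. When drop-out depends on predictors of outcome that the GEE model omits, the written weights typically enlarge arm-level bias. In the two-group illustration this is 5.3 to 17.6 points for a 40-point response gap, against 1.3 to 5.3 with no weighting and 0 with correct weights. A false contrast also needs a drop-out pattern that differs by arm. Under missing completely at random the written weights add no bias.

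The group splits, response gaps and simulation parameters are assumptions. They show direction and possible size and do not predict this trial's results. The practical reach is narrow: longitudinal analyses, if GEE is used, of non-normal continuous outcomes such as HBV DNA and of binary or count outcomes. The sentence should still be corrected, because it defeats the purpose of the method it describes.

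**What to change.** In section 8.2, replace the description of the GEE weight with: *each observed record is weighted by 1/(1 − p̂), where p̂ is its probability of being missing as fitted by the logistic model; that is, by the inverse of its estimated probability of being observed.* Cumulating the weights over visits and stabilising them are optional refinements.

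The cost is one line of SAP text. It needs no new data and leaves the primary analysis and the sample size unchanged.

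### The missing-data sensitivity analysis compares model fits by log-likelihood, which cannot separate MAR from MNAR, so as specified it does not test the primary result against MNAR dropout

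*Combined protocol and SAP*

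**What the plan says.** Section 8.2 (Missing data) gives the primary endpoint two analyses. One is a Kaplan-Meier estimate that keeps dropouts in for as long as they are followed. For the other, "we will also conduct the analysis of primary endpoint on the available cases", with stratified and covariate-adjusted versions.

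The section then sets out a general approach to missing outcomes. On MNAR it says: "It is unlikely that the probability of missing will depend on unobserved outcome and/or covariates". It continues: "However selection models such as MNAR Dale model and Diggle-Kenward model (23) can be used in such cases". On these models it adds: "These models often require strong assumptions on the dropout mechanism, which are primarily unverifiable based on the observed data".

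The aim of the sensitivity work is stated clearly: "We will conduct sensitivity analyses to investigate the sensitivity of our conclusion to possible violation of such assumptions". The method is to fit models under all three assumptions and "compare the model fits using log-likelihoods". The section gives no other criterion, no range of departures from MAR and no tipping point. It does not say that treatment-effect estimates will be set side by side.

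Section 8.3 (Sample size and power) expects about 25% loss to follow-up, 188 randomised per arm, and HBsAg loss of 5% on tenofovir DF alone against 15% on the combination.

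**The concern.** The aim and the method do not match. A log-likelihood is computed from observed data only. The paragraph says that the dropout assumptions mostly cannot be verified from observed data, and then makes observed-data fit its only stated comparison. For any MNAR model, an MAR model with the same observed-data fit can be constructed. If MAR and MNAR fits do differ, the difference comes from the parametric form imposed on the outcome and the dropout model.

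The practical risk is in reporting. A better likelihood for the MAR model could be presented as support for MAR, when it carries no such information. Meanwhile nobody would have asked how different the missing participants would need to be for the primary conclusion to change. The events are few (about 7 and 21 at the planned rates) and the planned missing number 47 per arm, so the question is worth asking.

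**Working it through.** **Inputs**, all from Section 8.3 (Sample size and power): 5% against 15%, two-sided 5% level, 80% power, 141 per arm before loss, 25% loss, 376 in total (188 per arm).

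**1. The plan's own figure.** With the pooled-variance chi-square formula, n = [1.960·√(2·0.10·0.90) + 0.842·√(0.05·0.95 + 0.15·0.85)]² / 0.10² = 1.1836² / 0.01 = 140.1, so 141 per arm. Then 282/0.75 = 376. Both reproduce. The planned missing number is 188 − 141 = 47 per arm.

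**2. Does log-likelihood move with the MNAR assumption?** Take the planned rates as observed counts: 7 of 141 (tenofovir DF) and 21 of 141 (combination). In an arm with e observed events, o observed and m missing, suppose a fraction q of the missing lost HBsAg. Then:

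- x = e + m·q and p = x/188;
- the chance of being observed is r1 = e/x for those with loss and r0 = (o − e)/(188 − x) for those without;
- the three likelihood terms are p·r1 = e/188, (1 − p)·r0 = (o − e)/188, and the probability of being missing, m/188.

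None of these contains q, so every value of q fits equally well. Numerically, the controls contribute −133.562 and the combination arm −165.060, a total of −298.622 in every row below. The rates in the missing are assumptions, not document figures, and the p-values treat the filled-in counts as observed.

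| Assumed loss in missing: control / combination | Difference | p | Log-likelihood |
|---|---|---|---|
| As observed (MAR) | 9.9 points | 0.005 (141 per arm) | −298.622 |
| 0% / 0% | 7.4 | 0.006 | −298.622 |
| 5% / 5% | 7.4 | 0.010 | −298.622 |
| 10% / 5% | 6.2 | 0.039 | −298.622 |
| 15% / 5% | 4.9 | 0.11 | −298.622 |

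Last row: control 7 + 47·0.15 = 14.05, combination 21 + 47·0.05 = 23.35, difference 9.30/188 = 4.9 points.

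**3. What if the selection model is parametric?** Likelihoods can then differ, so a two-visit Diggle-Kenward-type model was simulated: 376 participants, about 25% dropout, 200 replicates per scenario, likelihood-ratio test of MAR against MNAR at 3.84.

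- Normal outcome, dropout truly MAR: MNAR preferred in 8.5% of runs.
- Normal outcome, dropout truly MNAR (log-odds 0.5 per unit of the unseen value): MNAR preferred in 9.5%.
- Skewed (gamma) outcome, dropout truly MAR: MNAR preferred in 100%. The estimated second-visit intercept moved by about −0.35 residual SD, and the MNAR parameter diverged.

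The test hardly separated the two mechanisms when the model form was right. It responded strongly to the outcome distribution when the form was wrong. The simulation settings are illustrative choices.

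**4. Tipping counts** (uncorrected chi-square, 188 per arm, filled-in counts treated as observed).

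- No losses of HBsAg among the missing combination participants: 3 added control losses give 10 against 21, p=0.039. Four give 11 against 21, p=0.065. The threshold is 4/47 = 8.5%.
- Seven added combination losses (7/47 = 15%, the observed rate): 8 added control losses give 15 against 28, p=0.035. Nine give 16 against 28, p=0.054. The threshold is 9/47 = 19%.

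**The case against.** Several points on the other side stand.

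- A reader might infer that the plan selects one of the three models by likelihood. It says only that fits are compared. Its stated aim is sensitivity of the conclusion, and three fits would in practice give three effect estimates. What remains is that the plan never says those estimates will be reported or compared, and it names no other use for the fits.
- Log-likelihood is not useless across the board. MCAR against MAR concerns dependence on observed data, and fit can inform that part of the comparison. The failure is confined to MAR against MNAR.
- A reader might infer that the named selection models cannot handle the primary endpoint. That goes too far. The Dale model is for repeated categorical outcomes, and Sections 6.4 to 6.6 schedule qualitative HBsAg at weeks 48, 96, 180, 192, 216 and 240, so such a model could be built. The list of models is also open-ended. What stands is that the plan makes these models optional and does not connect them to the week-240 analysis.
- The text is general guidance for all outcomes, and the primary endpoint has its own analyses. But Kaplan-Meier, which Section 8.2 itself credits only with handling MCAR dropout, and available cases do not examine MNAR. The expectation of similar missingness in both arms does not help either, because equal rates do not imply equal outcomes among the missing.
- The fixed-table counts are not the planned analysis. Under Kaplan-Meier, someone lost late contributes most of their follow-up and any earlier loss of HBsAg. This limits the figures to illustration.

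**Conclusion.** The point holds in this form: the stated comparison cannot serve the stated aim where MNAR is concerned, and nothing else in Section 8.2 supplies an MNAR check of the primary result. It rests on the plan's wording and on a general property of observed-data likelihoods, shown here at the planned numbers. No sample-size figure is affected.

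A reader might infer from the tipping counts that the expected result is fragile. The documents do not support that. Counting every missing participant as no loss still gives p=0.006. Losing significance takes either missing controls above their observed 5% with no responder at all among 47 missing combination participants, or missing controls at nearly four times their observed rate if combination dropouts behave as observed. A proper analysis could therefore strengthen the conclusion. The counts assume exactly the planned rates, exactly 47 missing per arm, wholly unknown outcomes for them, and a simple two-by-two test.

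**What to change.** In Section 8.2, drop log-likelihood as the criterion for MAR against MNAR; it may stay as a description of MCAR against MAR. For HBsAg loss at week 240, prespecify multiple imputation under MAR using arm, the randomisation strata and on-study HBsAg, HBV DNA and ALT. Then apply delta adjustments to the odds of loss among the missing, varied separately by arm over a stated range, and report the treatment effect and 95% confidence interval at each setting and the tipping point.

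A smaller change would be to commit to reporting effects and intervals from the three fits already planned, with the MNAR model written explicitly for week-240 HBsAg status. That is an improvement, but it leaves the result dependent on one parametric dropout model.

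The imputation variables are already in the visit schedule. The cost is SAP wording and modest programming, with no change to sample size or trial conduct.

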8.3. Safety analysis

8.3.1. Adverse events

Summaries of adverse events (number adverse events, number and percentage of participants with adverse events, rates per person-years) will be provided by treatment

group. Events will be summarized based on the date of onset for the event. A treatment emergent adverse event will be defined as an adverse event that begins on or after the date of first dose of study drug. Events that occur prior to the first dose of study medication or after the last dose of study medication will be summarized separately. Summaries of the following are planned:

- all adverse events recorded between screening and first dose of study medication,
- all treatment emergent adverse events,
- all emergent and related adverse events,
- all treatment emergent renal adverse events,
- all treatment emergent and related renal adverse events
- combined Grade 2, 3 and 4 treatment emergent adverse events,
- combined Grade 2, 3 and 4 related treatment and emergent adverse events,
- combined Grade 3 and 4 treatment emergent adverse events,
- combined Grade 3 and 4 related treatment and emergent adverse events,
- all adverse events that caused permanent discontinuation of study drug,
- all adverse events that caused temporary interruption of study drug,
- all serious adverse events, and
- all serious and related adverse events.

In addition quarterly safety analysis will be reported to DSMB.

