2.2.3. Sustained off treatment (36 and 48 weeks after end of treatment) responses

- a. ALT \leq 38 U/L (males), \leq 25 U/L (females) corresponding to approximately 1.25 xULN.
- b. HBV DNA $<$ 1000 IU/mL.
- c. HBV DNA $<$ 1000 IU/mL AND ALT \leq 38 U/L (males), \leq 25 U/L (females) corresponding to approximately 1.25 xULN.
- d. HBV DNA $<$ 20 IU/mL (LLOQ of COBAS Ampliprep/COBAS TaqMan HBV v2.0 test).

2.2.4. Sustained off treatment (36 and 48 weeks after end of treatment) responses in participants with low end of treatment HBsAg levels ($<$ 2000 IU/mL) versus participants with high end of treatment HBsAg levels (\geq 2000 IU/mL)

- a. Cumulative HBsAg loss.
- b. HBeAg loss.
- c. HBsAg seroconversion.
- d. HBeAg seroconversion.
- e. ALT normalization (males \leq 30 U/L, females \leq 20 U/L).
- f. HBV DNA $<$ 1000 IU/mL.
- g. HBV DNA $<$ 20 IU/mL (LLOQ of COBAS Ampliprep/COBAS TaqMan HBV v2.0 test).

2.2.5. Sustained off-treatment (36 and 48 weeks after end of treatment) responses in participants with a substantial drop of HBsAg levels (\geq 1 log from baseline to end of treatment) versus participants who did not have substantial drop of HBsAg levels ($<$ 1 log from baseline to end of treatment)

- a. Cumulative HBsAg loss.
- b. HBeAg loss.
- c. HBsAg seroconversion.
- d. HBeAg seroconversion.
- e. ALT normalization (males \leq 30 U/L, females \leq 20 U/L).
- f. HBV DNA $<$ 1000 IU/mL.
- g. HBV DNA $<$ 20 IU/mL (LLOQ of COBAS Ampliprep/COBAS TaqMan HBV v2.0 test).

2.2.6. Sustained off-treatment (36 and 48 weeks after end-off treatment) responses in participants with end of treatment HBsAg level $<$ 2000 IU/mL and HBV DNA below 1000 IU/mL versus participants with end of treatment HBsAg levels \geq 2000 IU/mL and HBV DNA \geq 1000 IU/mL

- a. Cumulative HBsAg loss.
- b. HBeAg loss.

- c. HBsAg seroconversion.
- d. HBeAg seroconversion.
- e. ALT normalization (males \leq 30 U/L, females \leq 20 U/L).
- f. HBV DNA $<$ 1000 IU/mL.
- g. HBV DNA $<$ 20 IU/mL (LLOQ of COBAS Ampliprep/COBAS TaqMan HBV v2.0 test).

2.2.7. Treatment failure- Cumulative rates of primary nonresponse, partial virologic response and confirmed virologic breakthrough

2.2.8. Rate of discontinuation of treatment due to adverse events.

2.2.9. Rates of adverse events and serious adverse events.

3. Study design

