5.1. Dosage and administration

Participants will be randomly assigned to receive one of the following treatments during the treatment period of the study:

- Treatment A: Tenofovir DF 300 mg by mouth once daily for 192 weeks.
- Treatment B: Peginterferon alfa-2a 180 µg by subcutaneous injection once weekly in combination with tenofovir DF 300 mg by mouth once daily for 24 weeks followed by tenofovir DF 300 mg once daily for 168 weeks (192 weeks total therapy).

All participants will be instructed to take one tablet of tenofovir DF once daily without regards to meals. Participants in treatment arm B will also be instructed to take 180 µg of peginterferon alfa-2a subcutaneously once weekly. Participants in treatment arm B will be instructed to inject the peginterferon alfa-2a on the same day each week.

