Participants who do not meet criteria for discontinuing treatment will continue treatment with tenofovir DF until Week 240 or end of the study. Tenofovir DF for the period Week 192 to Week 240 will be provided by the study. Follow up visits and testing will continue every 12 weeks (204, 216, 228) to week 240 or end of the study. If tenofovir DF will be continued beyond Week 240 or end of the study, medication must be obtained per standard of care.

Participants who meet criteria for discontinuing treatment but continue treatment will have follow-up visits and testing per the schedule for participants who discontinue treatment. No study medications (Tenofovir DF) will be provided beyond Week 192 and any antiviral therapy must be obtained per standard of care.

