The dose of study medications may be decreased due to adverse events or laboratory abnormalities. The weekly dose of peginterferon alfa-2a will be reduced in graduated steps as follows:

- Level 1 decrease from 180 µg to 135 µg
- Level 2 decrease from 135 µg to 90 µg
- Level 3 decrease from 90 µg to 45µg

For participants who require a downward dose adjustment for neutropenia or thrombocytopenia, laboratory values should be repeated, if practical, prior to the next dose of peginterferon alfa-2a to confirm the result and dictate the course of action. Participants who remain with a neutrophil count below 500/mm³ (but above 250/mm³) or a platelet count below 50,000/mm³ (but above 25,000/mm³) should receive stepwise dose reductions until levels of neutrophils and platelets are $\geq 500/\text{mm}^3$ or 50,000/mm³, respectively, or until a dose of 45 µg of peginterferon alfa-2a is reached. Participants who have a neutrophil count below 250/mm³ or a platelet count below 25,000/mm³ should have their peginterferon alfa-2a dose held. Peginterferon alfa-2a may be resumed at the previous reduced dose when the neutrophil count has been above 500/mm³ or platelet count above 50,000/mm³ on 2 occasions at least 1 week apart.

7.2.c. Guidelines for subsequent peginterferon alfa-2a dose adjustments

Once a participant's dose has been decreased for laboratory abnormalities or adverse events, the study physician may attempt to increase the dose back to or toward the previous stable level only if the following conditions are satisfied:

1. The event or circumstance responsible for the dosage adjustment has resolved or improved;
2. The participant has been at the lower dose for ≤ 4 consecutive doses;
3. The participant had ≤ 6 total doses administered at the lower level during the entirety of the treatment period.

If four or more consecutive doses of peginterferon alfa-2a are held or otherwise not administered (i.e., the participant has not received test medication for more than 28 days), the participant will be considered intolerant of the test medication or non-compliant, whichever is more appropriate to the clinical situation. In such cases, the study physician will discontinue peginterferon alfa-2a but tenofovir DF treatment will continue.

Every attempt will be made to keep those participants randomized to treatment with peginterferon alfa-2a on therapy by dose reduction. The use of hematological growth factors during the study will not be allowed.

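### Section 8.3.1 does not separate adverse events in the 24-week peginterferon period from the tenofovir-only period, and Section 2.2.8 does not say whether stopping peginterferon alone counts

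*Combined protocol and SAP*

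**What the plan says.** Section 8.3.1 plans three measures by arm: number of events, and the "number and percentage of participants with adverse events, rates per person-years) will be provided by treatment" group. The window is set by "A treatment emergent adverse event will be defined as an adverse event that begins on or after the date of first dose of study drug". By time, only events before the first dose or "after the last dose of study medication will be summarized separately"; there is no other time split. The section assigns events by onset date but names no period, and it does not define the person-year denominator.

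Section 5.1 gives the combination arm peginterferon with tenofovir "for 24 weeks followed by tenofovir DF 300 mg once daily for 168 weeks (192 weeks total therapy". The control arm takes tenofovir throughout. Participants who do not meet the stopping criteria at week 192 stay on treatment: "Tenofovir DF for the period Week 192 to Week 240 will be provided by the study".

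Section 2.2.8 defines a secondary endpoint as "Rate of discontinuation of treatment due to adverse events" and names no drug. Section 7.2.c covers participants who miss at least four peginterferon doses in a row: "the study physician will discontinue peginterferon alfa-2a but tenofovir DF treatment will continue". Section 7.2.d likewise stops peginterferon but keeps tenofovir in certain cases of depression or suicidal or homicidal ideation. Section 8.3.1 separately plans a table of events leading to permanent stopping of study drug, and Section 5.4 counts peginterferon among the study drugs.

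**The concern.** The trial asks what a limited course of peginterferon adds to tenofovir. Its safety cost has to be weighed against any gain in HBsAg loss, and that cost should appear mainly while the drug is being given. A rate per person-year taken over the whole treatment period averages 24 weeks in which the arms differ with 168 weeks in which they are assigned the same drug. A reader of that table could conclude that the two regimens have similar adverse-event rates when they differed clearly during peginterferon.

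The same blurring touches tolerability. A participant who gives up peginterferon for an adverse event but stays on tenofovir could be counted, or not, as having discontinued treatment. Two analysts could report different values for a named secondary endpoint.

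**Working it through.** **The plan's own figures.** Section 5.1: 24 + 168 = 192 weeks. Section on sample size and power: 5% versus 15%, two-sided 5% level, 80% power, no continuity correction, gives 141 per arm; 282/(1 - 0.25) = 376, or 188 per arm. Both reproduce. The documents give no adverse-event rate and no safety power figure, so the background rates and rate ratios below are assumptions. Pooling over 192 weeks is inferred from the lack of any split; Section 8.3.1 does not state it.

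**Exposure.** 24/192 = 12.5%. With full follow-up, 188 x 24/52 = 87 of 188 x 192/52 = 694 person-years per arm.

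**Excess rate per person-year.** Let b be the background rate and r the true ratio in weeks 0-24, with no excess afterwards.
- Excess in weeks 0-24: b(r - 1).
- Pooled over 192 weeks: b(r - 1) x 24/192, one-eighth.
- Pooled over 240 weeks: 24/240, one-tenth.
- With 25% lost at a constant rate by week 240, mean follow-up is 23.7 weeks within weeks 0-24 and 171.5 weeks to week 192; 171.5/23.7 = 7.2, about one-seventh.

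**Rate ratio.** Pooled ratio = (24r + 168)/192.
- r = 2: 216/192 = 1.13
- r = 3: 240/192 = 1.25
- r = 5: 288/192 = 1.50

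**Counts.** With b = 0.25 per person-year, r = 3 and 188 per arm, weeks 0-24 give about 65 versus 22 events and 192 weeks give 216 versus 173. The excess is 43 both times, so counts are not diluted.

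**Percentage of participants.** With a constant background hazard and the excess confined to weeks 0-24, the week 0-24 difference divided by the 192-week difference is exp(b x 168/52.18). The rate ratio cancels from this factor; the differences below use r = 3.

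| b per person-year | Difference, weeks 0-24 (points) | Difference, 192 weeks (points) | Shrinkage |
|---|---|---|---|
| 0.01 | 0.9 | 0.9 | 1.03-fold |
| 0.10 | 8.4 | 6.1 | 1.4-fold |
| 0.25 | 18.3 | 8.2 | 2.2-fold |
| 0.50 | 29.3 | 5.9 | 5.0-fold |
| 0.65 | 33.4 | 4.1 | 8.1-fold |

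**Endpoint 2.2.8.** Section 5.3.3 cites discontinuation in 6% to 9% of participants in the hepatitis B registration trials. 0.06 x 188 = 11.3 and 0.09 x 188 = 16.9, so about 11 to 17 participants.

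**The case against.** A reader might infer that peginterferon's harm as a whole is diluted eight-fold. The documents do not support that. Section 8.3.1 reports three measures, and the factor of eight belongs only to the excess person-year rate. For uncommon events, percentages hardly change: with an assumed 10% background over 192 weeks and a 5-point excess risk in weeks 0-24, the difference is 4.9 points in the window (6.2% versus 1.3%) and 4.5 points pooled (14.5% versus 10%).

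A reader might also cite lost power. On those same assumptions a two-proportion test with 188 per arm has 26% power pooled and 71% in weeks 0-24. But Section 8.3.1 plans summaries, not tests, and the rates are invented for illustration. Nor is a person-year rate invalid because the hazard changes: it is a legitimate average, only an uninformative one here.

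On 2.2.8 it is tempting to say that peginterferon-only stops would be lost. They need not be. The study-drug discontinuation table can capture them, although it is not split by drug and does not define the endpoint. The protocol also uses the word treatment for a single drug, so a narrow reading is not compelled. The 11-17 is an upper figure: Section 5.3.3 gives neither course length nor reasons for stopping, some stops would end all treatment under Sections 6.13.1 and 7.1, and the 7.2.c route includes non-compliance.

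Other offsets are real. Summaries of related events are planned, the DSMB sees data by arm in closed reports, and onset dates are used, so the split could still be made at reporting. But related-event summaries depend on the investigator's attribution and have no period split either. Reading the last dose drug by drug would separate later events in the combination arm, but the text does not say so, and the control arm would have no matching date.

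**Conclusion.** The gap stands in a limited form. Section 8.3.1 has no split between the peginterferon and tenofovir-only periods, and its person-year comparison would understate an excess confined to weeks 0-24: about one-eighth of its size in that period (one-seventh to one-tenth across the follow-up assumptions shown), with a ratio of 3 appearing as 1.25. This assumes that the excess falls within weeks 0-24; any excess that persists would reduce the dilution. Counts are unaffected, and percentages are affected little for rare events and heavily for common ones.

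The 2.2.8 problem is an ambiguous definition, not missing safety data. Up to about 11-17 of 188 participants could depend on the reading, as an indication only. Neither point touches the sample size or the primary analysis.

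**What to change.** - In Section 8.3.1, keep the overall summaries and add the same ones by arm for weeks 0-24 and for after week 24, using study weeks in both arms and assigning events by onset date.
- Define person-time for each period and for the overall rate, including how time after week 192 is treated.
- If events soon after the last peginterferon dose are to be included in the first period, fix the lag in advance and use it consistently in both arms. A lag has a price: if it adds no excess, a 36-week window shows a ratio of 3 as (3 x 24 + 12)/36 = 2.33.
- Report 2.2.8 in two rows: any study drug, including peginterferon alone, permanently stopped for an adverse event; and all study treatment stopped for an adverse event.

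The cost is more table columns and fewer events in each period, so less precise estimates by period. No new data are needed.
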